Cover Page:

Title: Evaluation of AI-based Risk Assessment Model in Plastic Surgery

NCT Number: [NCT ID not yet assigned]

Document Date: July 11, 2024

Document Review Statement:

This document was most recently updated and reviewed by the sole researcher, [name], EMBA, on July 11, 2024. As there is no human subjects protection review board required for this study, this date reflects the most recent review and update by the principal investigator.

Study Protocol

Introduction

This study protocol outlines the procedures, objectives, and methodologies for the observational study titled "Evaluation of AI-based Risk Assessment Model in Plastic Surgery." The primary aim is to evaluate the clinical utility of an AI-based risk assessment model in predicting and mitigating complications in patients undergoing elective plastic surgery.

Study Objectives

- To evaluate the effectiveness of the AI-based risk assessment model in predicting surgical complications.
- To determine the correlation between various clinical factors (such as BMI, age, and smoking habits) and the AI-generated risk scores.
- To assess the impact of AI-generated recommendations on surgical outcomes and complication rates.

Study Design

This is an observational study with a prospective time perspective. The study involves the collection of clinical data from patients undergoing elective plastic surgery. The AI model analyzes this data to provide personalized risk scores and recommendations.

Participant Eligibility

Inclusion Criteria:

- Individuals aged 18 and older.
- Scheduled to undergo elective plastic surgery.
- Agreement to follow preoperative and postoperative recommendations provided by [name], according to the AI-based risk assessment model.

Exclusion Criteria:

- Individuals below 18 years of age.
- Patients with a history of severe allergic reactions to anesthesia.
- Those unable to provide informed consent.

Study Population Description

Participants are individuals undergoing elective plastic surgery. They will complete an online form collecting data on various clinical factors, such as age, height, weight, smoking habits, and comorbidities. The system calculates the risk score, body mass index (BMI), and Caprini score.

Data Collection

The following data will be collected from each participant:

- Age
- Height and weight (to calculate BMI)
- Smoking habits
- Comorbidities
- Caprini score (calculated by the system)

- Risk group classification (High, Moderate, Low)

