- Complications (Hematoma, Seroma, Infection, Dehiscence, Necrosis, DVT/PE, ASIA Syndrome)

Study Procedures

Participants will undergo a risk assessment using the AI model, which evaluates multiple risk factors based on their clinical data and patient history. The model will then generate personalized recommendations, which include:

- Weight management guidance for patients with a BMI greater than 25.1.
- Smoking cessation advice for patients who smoke.
- Blood pressure control recommendations for hypertensive patients.
- Doppler ultrasound screening for deep vein thrombosis (DVT) and varices.
- Nutritional consultations for patients with a BMI of 25.1 or lower.
- Specialist referrals based on comorbidities and psychiatric consultations for Body Dysmorphic Disorder (BDD) screening.

Follow-Up

The follow-up period for this study ranges from 2 to 41 months, with a mean follow-up of 15 months. During this time, data on patient outcomes, including complication rates and patient satisfaction, will be collected and analyzed.

Outcome Measures

Primary Outcome Measure

Title: Incidence of complications within 45 days post-surgery

Description: The primary outcome measure is the incidence of complications (such as hematoma, seroma, infection, etc.) occurring within 45 days after elective plastic surgery. Complications are identified and recorded based on clinical follow-up visits and patient reports.

Conclusion

This study protocol provides a comprehensive overview of the study design, objectives, data collection methods, and statistical analysis plan for the observational study "Evaluation of AI-based Risk Assessment Model in Plastic Surgery." The integration of AI-generated recommendations is expected to enhance preoperative planning and postoperative care, ultimately improving patient safety and satisfaction.

Statistical Analysis Plan (SAP)

Introduction

This Statistical Analysis Plan (SAP) outlines the statistical methods and analyses to be performed for the study titled "Evaluation of AI-based Risk Assessment Model in Plastic Surgery." The primary aim of the study is to assess the clinical utility of an AI-based risk assessment model in identifying and mitigating risk factors associated with complications in patients undergoing elective plastic surgery.

Study Objectives

- To evaluate the effectiveness of the AI-based risk assessment model in predicting surgical complications.

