- To determine the correlation between various clinical factors (such as BMI, age, and smoking habits) and the AI-generated risk scores.
- To assess the impact of AI-generated recommendations on surgical outcomes and complication rates.

Study Design

This is an observational study with a prospective time perspective. The study involves the collection of clinical data from patients undergoing elective plastic surgery. The AI model analyzes this data to provide personalized risk scores and recommendations.

Data Collection

The following data will be collected from each participant:

- Age
- Height and weight (to calculate BMI)
- Smoking habits
- Comorbidities
- Caprini score (calculated by the system)
- Risk group classification (High, Moderate, Low)
- Complications (Hematoma, Seroma, Infection, Dehiscence, Necrosis, DVT/PE, ASIA Syndrome)

Primary Outcome Measure

Title: Incidence of complications within 45 days post-surgery

Description: The primary outcome measure is the incidence of complications (such as hematoma, seroma, infection, etc.) occurring within 45 days after elective plastic surgery. Complications are identified and recorded based on clinical follow-up visits and patient reports.

Statistical Methods

The following statistical methods and formulas will be used for data analysis:

Descriptive Statistics:

- Frequency and percentage of patients in each risk group (High, Moderate, Low)
- Incidence of complications in each risk group

- Relative risk and odds ratio for complications in each risk group

Pearson Correlation:

- Correlation between risk factors (Age, BMI, Smoking habits, etc.) and AI-generated risk scores

python

Copiar código

```
stats.pearsonr(corr4['Risk factor'], corr4['BMI'])

stats.pearsonr(corr4['Risk factor'], corr4['Caprini score'])

stats.pearsonr(corr4['Risk factor'], corr4['Age'])

stats.pearsonr(corr4['Risk factor'], corr4['Smoking habit'])

stats.pearsonr(corr4['Risk factor'], corr4['Male'])

stats.pearsonr(corr4['Risk factor'], corr4['Female'])

stats.pearsonr(corr4['Risk factor'], corr4['High blood pressure'])
```

Outcome Analysis:

- Count and percentage of complications in each risk group
- Calculation of relative risk and odds ratio

python

Copiar código

Relative Risk = (Incidence in high-risk group) / (Incidence in low-risk group)

Odds Ratio = (Odds of complications in high-risk group) / (Odds of complications in low-risk group)

Data Analysis

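### The Pearson correlations mostly set the AI score against its own inputs, so they describe how the score is built and are not evidence that it predicts complications

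*Combined protocol and SAP*

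**What the plan says.** The second objective, in both the protocol and the SAP, is "To determine the correlation between various clinical factors (such as BMI, age, and smoking habits) and the AI-generated risk scores". The SAP serves it under Statistical Methods, Pearson Correlation, where the planned analysis is "Correlation between risk factors (Age, BMI, Smoking habits, etc.) and AI-generated risk scores", carried out with seven calls. One begins "stats.pearsonr(corr4['Risk factor'], corr4['BMI"; the others use the Caprini score, age, smoking, male, female and high blood pressure. The column named Risk factor is the constant first argument, and I take it to be the AI score. No call uses complications.

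On where the score comes from:

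- Protocol, Study Population Description, on participants: "They will complete an online form collecting data on various clinical factors, such as age, height, weight, smoking habits, and comorbidities". Then: "The system calculates the risk score, body mass index (BMI), and Caprini score".
- Study Design, in both parts: "The AI model analyzes this data to provide personalized risk scores and recommendations".
- Protocol, Study Procedures, on the model: "which evaluates multiple risk factors based on their clinical data and patient history".

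Under Descriptive Statistics and Outcome Analysis, the SAP separately tabulates complications by the three-level risk group and defines a relative risk and an odds ratio, high against low. These are bare formulas, with no confidence interval or test stated.

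**The concern.** When a score is computed from a variable, testing whether the two are uncorrelated asks nothing about patients' outcomes. The coefficient reflects the weight the software gives that variable and how much it varies in this clinic. The pearsonr function also returns a p-value, and these are the only p-values that the written SAP would produce.

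The SAP's Conclusion presents the whole analysis as informing the model's effectiveness in predicting and mitigating complications, and nothing marks the Pearson block as purely descriptive. A table of strong, significant correlations could therefore be read as support for the model although it carries no information on outcome. Meanwhile the continuous score and the individual factors are never set against 45-day complications.

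**Working it through.** The plan states no expected correlation, sample size, alpha or event rate, so there is no figure of its own to reproduce. The check has three steps.

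**1. Which correlates are inputs?**

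| Correlate | What the documents show |
|---|---|
| Age, smoking | On the form; the model analyses these data |
| BMI | Computed by the system from form height and weight |
| High blood pressure | Very probably an input, as a comorbidity; it also triggers a recommendation |
| Caprini score | Not a form field; computed by the same system |
| Male, female | Not on the data-collection list; not shown to be an input |

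If male and female are two complementary indicators, their coefficients differ only in sign and one call is redundant.

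**2. Closed form.** For a score S = Σ wⱼXⱼ with independent inputs, the correlation with input i is

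r = wᵢσᵢ / √(Σ wⱼ²σⱼ²).

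Complications do not appear in it. The chance of p<0.05 (Fisher z, upper tail) is about Φ(atanh(r)·√(n−3) − 1.96).

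- Six equally weighted inputs: r = 1/√6 = 0.41. The chance is 84% at n = 50, 99% at n = 100 and 100% at n = 200.
- Assumed score: standardised age + standardised BMI + one point each for smoking and hypertension, each at 15% prevalence. The variance is 1 + 1 + 2 × (0.15 × 0.85) = 2.255. For age or BMI, r = 1/√2.255 = 0.67. For smoking or hypertension, r = √(0.1275/2.255) = 0.24 and atanh(r) = 0.242. At n = 200: 0.242 × √197 − 1.96 = 1.44, giving 93%. At n = 100: 0.242 × √97 − 1.96 = 0.43, giving 67%.
- The sample size for 80% power is 30 at r = 0.5, 85 at r = 0.3, 194 at r = 0.2 and 783 at r = 0.1. Weakly weighted inputs can therefore miss significance.

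**3. Simulation**, 2,000 data sets per scenario, with complications drawn independently of the score. For the second score in step 2, with 12% complications and n = 200, p<0.05 occurred in 100% of runs for age and BMI, 92% to 93% for smoking and hypertension, and 5% for score against complications. At n = 100 the figures were 100% and 100%, then 68% and 66%, then 5%.

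A wider set covered all seven correlates. It assumed 10% complications, smoking and hypertension 15% each, male 12%, and risk groups as tertiles of the score:

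| Score | N | BMI, Caprini, age | Smoking, hypertension | Male, female |
|---|---|---|---|---|
| Equal weights, sex included | 50 | 98–100% | 73% | 72% |
| Same | 100 | 100% | 96% | 97% |
| Same | 200 | 100% | 100% | 99.9% |
| Equal weights, sex not an input | 100–500 | 100% | 98–100% | about 5% |
| Light weights on smoking and hypertension (r about 0.08), other components added, sex not an input | 100 | 100% | about 12% | 6% |
| Same | 200 | 100% | 21% | 5% |
| Same | 500 | 100% | 43% | 5% |

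Across all of these, score against complications reached p<0.05 in 4.4% to 5.9% of runs. High against low risk group did so in 2.7% to 6.8%, with a median relative risk of 1.00 to 1.03. Testing against the outcome does not reward a score that predicts nothing; correlating with the main inputs does.

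**The case against.** The strongest defence is that Objective 2 is worded only as a correlation aim and the Pearson block does what it says. Prediction is Objective 1, and the SAP addresses it by comparing complications between risk groups. No passage sets an alpha or treats a correlation as validation, and showing how an undisclosed score varies with patient characteristics is legitimate. All of this stands. It is why the coefficients can stay, and why the point concerns labelling and a missing companion analysis.

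Three stronger readings are tempting, and the documents do not support them:

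- *All seven correlations will be significant whatever the model is worth.* This depends on weights and a sample size that are not given. Sex is not a listed input, and the Caprini score is a sister output, not a form field.
- *The model is never tested against complications.* That is true of the Pearson block only. The risk-group incidence, relative risk and odds ratio are such a comparison, though they use the score only as categories.
- *The SAP aims to find risk factors for complications and forgot to.* The aim stated in the SAP's Introduction is the model's clinical utility in identifying and mitigating such factors. No objective asks for a stand-alone factor analysis, so a regression on the factors is a useful addition and not an omitted primary analysis.

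One further objection limits the remedy. BMI, smoking and blood pressure are targets of the recommendations, which participants agree to follow as a condition of entry. Their associations with complications may be weakened because the recommendations worked, so a factor regression cannot by itself discredit the score.

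**Conclusion.** The point holds in limited form. The Pearson block is largely circular: it relates the score to data from which it is, or very probably is, calculated, and to a second score from the same system. Significant coefficients for the main inputs are expected even from a score with no relation to outcome. In the simulations BMI, Caprini score and age were significant in 98% to 100% of studies at every size from 50 to 500, while the same score was associated with complications at about the nominal 5%. For smoking and hypertension the range was 12% to 100%, depending on weight and sample size. These percentages rest on assumed weights, prevalences, event rate and sample size. The reasoning that the coefficients carry no information on outcome does not.

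The primary outcome is unaffected. The plan should be changed because, as written, one of three objectives yields results open to being misread as validation, and the score itself is not related to 45-day complications.

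**What to change.** In the SAP:

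1. Report the Pearson coefficients without p-values, label them a description of score composition, and state that they are not validation. Keep one sex indicator if the two are complementary.
2. Relate the score itself to any 45-day complication: discrimination and calibration, each with a confidence interval. The documents do not give the score's scale; if it is not a probability, show observed complication risk across the range of the score.
3. As a secondary exploratory analysis, report penalised (Firth) odds ratios for age, BMI, smoking and high blood pressure, with the number of terms fixed in advance by a stated rule on event count.
4. State that the odds ratios are associations under care guided by the model's recommendations, so a weak association does not show that the score weights a factor wrongly. The same caution applies to the score's own performance in item 2.

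The cost is SAP wording and a few lines of Python on data already collected. The correlation table can then no longer be presented as a positive result. The added estimates may be imprecise: at an assumed 10% complication rate, 100 patients give 100 × 0.10 = 10 events and 200 give 20.

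### The SAP does not measure how well the AI score discriminates 45-day complications or whether it adds to the Caprini score; their planned correlation is descriptive and cannot show either.

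*Combined protocol and SAP*

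**What the plan says.** The prediction aim stands first under Study Objectives in both the protocol and the SAP: "To evaluate the effectiveness of the AI-based risk assessment model in predicting surgical complications".

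On where the scores come from, the protocol's Study Population Description says of participants: "They will complete an online form collecting data on various clinical factors, such as age, height, weight, smoking habits, and comorbidities". The next sentence reads: "The system calculates the risk score, body mass index (BMI), and Caprini score". The Data Collection lists in both parts repeat "Caprini score (calculated by the system)". No separate scoring by a clinician is described. Under Study Procedures, the AI model is said to be one "which evaluates multiple risk factors based on their clinical data and patient history". Its formula and weights are not given, nor whether Caprini is one of its inputs.

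In the SAP's Statistical Methods, Caprini appears in one line of code, "stats.pearsonr(corr4['Risk factor'], corr4['Caprini score'])". It is one of seven correlations listed under "Correlation between risk factors (Age, BMI, Smoking habits, etc.) and AI-generated risk scores". None of the seven involves a complication variable.

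Complications are analysed under Descriptive Statistics and Outcome Analysis: counts and percentages by AI risk group, a relative risk and an odds ratio. One bullet mentions these ratios for each risk group, but the only formulas given compare high with low, for example "Relative Risk = (Incidence in high-risk group) / (Incidence in low-risk group)".

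**The concern.** A prediction objective calls for a measure of how well the score separates patients who have a complication from those who do not. A ratio of the high to the low group uses two of the three categories, leaves out the moderate group and discards the ordering of the score within groups. It can show that risk differs between the extremes, but not how well the score discriminates overall.

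The one analysis that brings in a second score does not fill this gap. The AI and Caprini scores are produced by the same system after the same form, so some agreement is likely wherever their inputs overlap. A sizeable r could be read as support for the AI score although the outcome plays no part in it. Whether the AI score says anything about 45-day complications beyond what Caprini already says would stay unexamined, although both scores and the outcome are on the data list.

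**Working it through.** **Plan's own figures.** The documents give no sample size, power, event rate, expected correlation or AUC, so there is nothing to reproduce. The check has three parts.

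**1. Trace of each variable through the SAP**

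| Analysis | AI score or group | Caprini | Complications |
|---|---|---|---|
| Frequency of risk groups | yes | no | no |
| Seven Pearson correlations | yes | one of the seven | no |
| Incidence by risk group | yes | no | yes |
| RR and OR, high over low | yes, two of three groups by formula | no | yes |

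No row holds both Caprini and complications. No AUC, calibration, or model with both scores is planned.

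**2. Can the correlation stand in for a prediction analysis?** All inputs here are assumed. Take two unweighted five-item scores that share k independent items of equal variance. Their covariance is k and each variance is 5, so r = k/5. Simulating 200,000 patients gave r = 0.20, 0.40, 0.60, 0.80 and 1.00 for k = 1 to 5.

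Complications were then generated from a logistic model with intercept -2.3 and, where a score mattered, a log odds ratio of 0.7 per standard deviation of that score. This gives event rates of about 9% to 11%. For k = 3:

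| Complications depend on | r | AUC, AI | AUC, Caprini-like |
|---|---|---|---|
| neither score | 0.60 | 0.505 | 0.503 |
| Caprini-like score only | 0.60 | 0.609 | 0.683 |
| AI score only | 0.60 | 0.683 | 0.613 |

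The same r goes with a useless AI score, one that is worse than Caprini and one that is better. This must be so, because r is computed without the outcome.

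**3. What precision could the added analysis have?** Again all inputs are assumed. For an AUC of a with n1 events and n0 non-events, the Hanley-McNeil variance is

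SE² = [a(1 - a) + (n1 - 1)(q1 - a²) + (n0 - 1)(q2 - a²)] / (n1·n0), with q1 = a/(2 - a) and q2 = 2a²/(1 + a).

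For two AUCs on the same patients, SE(diff)² = s1² + s2² - 2ρ·s1·s2, where ρ is the correlation between the two AUC estimates.

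Worked case: 570 patients, 10% event rate (n1 = 57, n0 = 513), AUCs 0.75 and 0.65, ρ = 0.6.
- s1 = 0.0385, so the 95% CI for the AI AUC is 0.75 ± 1.96 × 0.0385 = 0.75 ± 0.076.
- s2 = 0.0411.
- SE(diff) = √(0.0385² + 0.0411² - 2 × 0.6 × 0.0385 × 0.0411) = 0.0357.
- 0.10/0.0357 = 2.80 and 2.80 - 1.96 = 0.84, which is 80% power at two-sided 0.05.

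Patients (events) needed for 80% power, with ρ from 0.6 down to 0.3:

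| Event rate | AUC 0.75 v 0.65 | AUC 0.70 v 0.65 |
|---|---|---|
| 5% | 1,105 to 1,930 (55 to 96) | 4,570 to 7,995 (228 to 400) |
| 10% | 570 to 995 (57 to 100) | 2,365 to 4,135 (236 to 414) |
| 20% | 310 to 535 (62 to 107) | 1,280 to 2,235 (256 to 447) |

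**The case against.** **The correlation is not offered as validation.** This stands. The SAP lists it beside BMI, age, sex and blood pressure, and it serves the second objective, on clinical factors and AI scores. A reader might infer that the plan means to validate the AI score against Caprini. Nothing in the text says so, and r does carry some information, namely how far the two scores agree.

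**The overlap in inputs is unknown.** This also stands. The form items are given as examples, the AI model also draws on patient history, and neither score's content is listed. It would be tempting to say that a positive correlation is guaranteed. The documents support only that it is expected to the extent that inputs are shared, and the simulated range of 0.20 to 1.00 shows how much depends on that.

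**Beating Caprini is not an objective, and the documents do not say what Caprini is meant to predict.** Correct. This is a gap against the prediction and clinical-utility aims, not a contradiction, and the comparison with Caprini belongs in the plan as exploratory. The need for a discrimination measure of the AI score itself does not depend on Caprini.

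**A high r does not show that the AI score is inferior.** One can build a case where the AI score is Caprini plus irrelevant noise. If Caprini's AUC is 0.70 and the noise variance equals the Caprini variance, r = 1/√2 = 0.71 and the AI score's AUC is Φ(0.524/√2) = 0.645. That assumes its conclusion. Even then the AI score adds nothing once Caprini is known; it does not subtract. Nothing in the documents says that the AI score is such a copy.

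**Outcomes may be altered by the recommendations.** Participants agree to follow AI-based recommendations, which may lower complications most where the AI score is high and so weaken its observed discrimination. This is a real limit on any AUC, but it affects the planned RR and OR as well.

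**Conclusion.** The point holds as a gap in the analysis. The AI groups are related to complications, so prediction is not wholly unaddressed, but a high-over-low ratio is a thin answer to the first objective, and nothing planned measures discrimination or the AI score's addition to Caprini. The Caprini correlation cannot supply either. In the illustration, r = 0.60 is compatible with an AI AUC of about 0.50, 0.61 or 0.68.

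The tracing of variables rests on the text alone. The sizes rest on assumed score structures, event rates and AUCs, and are not estimates for this study. The linked analysis notebook is not part of the documents and could not be checked. The change is worth making before analysis; its absence does not invalidate what is already planned.

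**What to change.** 1. In Pearson Correlation, label the Caprini correlation as descriptive. State which inputs the two scores share and whether Caprini is itself an input to the AI model.
2. In Outcome Analysis, add the AUC with 95% CI of the AI score for any complication within 45 days, using all patients, including the moderate group.
3. As an exploratory comparison on the same patients, add the AUC of Caprini, the paired difference with its 95% CI (DeLong or bootstrap), and a logistic model with Caprini alone against Caprini plus AI score (likelihood-ratio test).
4. Report the interval for the AUC difference as the main exploratory result, not only a p-value, and state that agreed adherence to AI-based recommendations may weaken the observed discrimination.

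The cost is a few lines of Python on fields already on the data list. There are two downsides. Without a stated sample size or event rate, the intervals may be too wide to settle the comparison; under the assumptions above, a difference of 0.10 in AUC needs from 310 to 1,930 patients. The result may also be less favourable to the AI model than a correlation or a ratio of extremes.

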Data analysis will be performed using Python, and the complete notebook with the analysis code and results is available at the following link: [Colab Notebook](#).

Access Instructions

To request permission to access the individual participant data (IPD) and supporting information, please email [contact]. Detailed instructions for requesting access can be found at [IPD Sharing Instructions](#).

Conclusion

This SAP provides a detailed plan for the statistical analysis of the study "Evaluation of AI-based Risk Assessment Model in Plastic Surgery." The analysis aims to provide insights into the effectiveness of the AI model in predicting and mitigating surgical complications, ultimately improving patient outcomes and safety.

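### Do the SAP's risk-group percentages, RR and OR lack a fixed time window and counting unit?

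*Combined protocol and SAP*

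**What the plan says.** The SAP's Primary Outcome Measure section reads: "The primary outcome measure is the incidence of complications (such as hematoma, seroma, infection, etc.) occurring within 45 days after elective plastic surgery". Statistical Methods comes next. Under Descriptive Statistics it lists "Frequency and percentage of patients in each risk group (High, Moderate, Low"), then incidence, RR and OR by risk group. Under Outcome Analysis it lists "Count and percentage of complications in each risk group" and gives two formulas: RR as high-risk incidence over low-risk incidence, and OR as the corresponding ratio of odds. None of these lines names a window, or says how to count a patient with more than one complication.

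The Data Collection section, in both the protocol and the SAP, records "Complications (Hematoma, Seroma, Infection, Dehiscence, Necrosis, DVT/PE, ASIA Syndrome").

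Three other statements bear on the point:

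- The protocol's Follow-Up section says "The follow-up period for this study ranges from 2 to 41 months, with a mean follow-up of 15 months" and continues "During this time, data on patient outcomes, including complication rates and patient satisfaction, will be collected and analyzed".
- The third study objective is "To assess the impact of AI-generated recommendations on surgical outcomes and complication rates", with no window.
- The SAP's Data Analysis section says that "the complete notebook with the analysis code and results is available".

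**The concern.** Three things seem to be left open.

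- **Window.** The outcome is defined at 45 days, but the protocol also speaks of complication rates during a follow-up that differs widely between patients, and the SAP gives no person-time or time-to-event method. If the RR pooled all follow-up, its percentages would have no common time base.
- **Unit.** The SAP speaks of patients when it describes group sizes and of complications when it describes the outcome. Taken literally, the outcome line could mean affected patients over group size, events over group size, or each group's share of all complications.
- **Event list.** The outcome description gives examples and trails off, whereas the data list names seven types.

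At stake are the RR and OR, which compare the model's high-risk and low-risk groups. If window and unit were really free, one data set could give several answers. Because results already exist, a reader could not tell which answer had been planned.

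**Working it through.** The documents give no sample size, event rate, alpha or power, so there is no figure of the plan to reproduce. The check is a reading of the text plus some arithmetic.

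**1. Is the 45-day analysis feasible on the stated follow-up?** Inputs: 45 days (Primary Outcome Measure); 2 to 41 months, mean 15 (Follow-Up); 30.4375 days per month.

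- Minimum follow-up: 2 × 30.4375 = 60.9 days, which exceeds 45.
- If follow-up is counted from surgery, every patient has a complete 45-day window. A simple proportion then needs no adjustment for follow-up length.

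**2. What would counting events do?** With the same patients in the denominators, RR(events) / RR(patients) = (mean events per affected high-risk patient) / (mean events per affected low-risk patient).

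- Equal means give a ratio of 1, so the RR is unchanged.
- Means of 1.0 in one group and 1.5 in the other (assumed) give 1.0/1.5 = 0.67 or 1.5/1.0 = 1.50.
- Example (assumed): 100 patients per group, 20 and 10 affected. By patients, RR = 0.20/0.10 = 2.00 and OR = (20/80)/(10/90) = 2.25.
- With 1.5 events per affected high-risk patient and 1.0 per affected low-risk patient, the counts are 30 and 10. RR = 0.30/0.10 = 3.00 and OR = (30/70)/(10/90) = 3.86.
- With 5 events per affected high-risk patient, which seven types allow, the count is 20 × 5 = 100 events in 100 patients. The odds would be 100/0, which is undefined.

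The last line bears on the reading. An OR makes sense only when each patient is a yes or a no, so planning one points to a patient-level outcome.

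**3. What would pooling all follow-up do?** Assume 45-day risks of 20% and 10%, then an equal late rate r per month in both groups over 15 months. Time after the window is 15 − 45/30.4375 = 15 − 1.48 = 13.52 months.

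- r = 0.2%: high 1 − 0.8·exp(−0.002 × 13.52) = 0.221; low 1 − 0.9·exp(−0.002 × 13.52) = 0.124; RR = 1.78.
- r = 1%: high 0.301; low 0.214; RR = 1.41.

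Window and unit would therefore matter if an analyst departed from the natural reading.

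**4. Does the text invite that departure?**

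| Element | Where the SAP settles it |
|---|---|
| Window | Its only defined outcome is at 45 days, immediately before the methods. It sets no other window. |
| Link to RR | The outcome is an incidence and the RR is a ratio of incidences. |
| Unit | RR and OR in risk groups are ordinarily patient-level, and odds require it. |
| Event list | The data list names seven types. No eighth appears anywhere. |

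The Follow-Up sentence says what is collected and analyzed during follow-up. It does not say that the risk-group RR or OR use all of that time.

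**The case for a change.** The strongest argument for a change is that silence is harmless only when nothing competes with it. Here the protocol promises an analysis of complication rates during long follow-up, an objective repeats the phrase without a window, and the outcome line switches from patients to complications. Either the risk-group statistics also cover the long period, or that longer analysis has no method. A notebook that already holds results cannot stand in for a written definition, and two or three sentences would settle the matter.

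Part of this stands. No methods line restates 45 days, no rule covers a patient with several complications, and no method is given for complications after day 45. The rest carries less weight:

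- The Follow-Up sentence can be read as early complications plus later satisfaction. A missing method for later complications does not alter the 45-day RR.
- Follow-up differs up to 41/2 = 20.5-fold between individual patients, and 45 days is 1.48/15 = 9.9% of its mean. Neither figure biases a 45-day proportion, and neither compares risk groups.
- RR and OR do not stand alone: incidence in each of the three risk groups is also planned, so separation is visible without them.
- The notebook's window and unit are not shown. The existence of results raises a question about the timing of the plan, separate from whether the RR is defined, and it is no evidence of selective choice.

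**Conclusion.** The concern is accurate about the wording but does not call for a change to the plan. The SAP omits a cross-reference and a counting rule that an analyst would normally supply correctly: patients with at least one of the seven listed complications within 45 days, over the patients in the risk group. On that reading the analysis is valid, and differences in follow-up length after day 45 do not affect it.

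The actual size of any distortion cannot be derived from the documents. The illustrative shifts (RR 2.00 to 3.00 by counting events; 2.00 to between 1.78 and 1.41 by pooling 15 months) rest wholly on assumed rates and on an analyst departing from the natural reading.

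The conclusion assumes that follow-up starts at surgery, which the documents do not state, and that complications up to day 45 are ascertained as described, through visits and patient reports. Missed visits are not addressed, but that is a different matter from the definition of the RR. The conclusion would need revisiting only if the reported figures turned out to use another window or unit.
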